12.2.13. Safety Analyses

All safety summaries and analyses will be based upon the Safety Population as defined in Section [12.2.1](#).

Overall exposure to study drug, the numbers of patients completing each cycle, and the dose intensity will be summarized using descriptive statistics. The number of patients with any dose adjustment will be presented for entire treatment period as well as for each cycle. The number of patients with dose reductions, dose delays, or dose omissions will also be summarized, as will the reasons for dose adjustments.

Adverse events will be reported using the MedDRA dictionary. Investigators will report a verbatim AE term and a CTCAE v4.0 term and severity for all AEs. For analysis purposes, the following process will be used:

- The CTCAE v4 term reported by the investigator will be mapped to the MedDRA Preferred Term (PT) and System Organ Class (SOC) using the corresponding MedDRA Lower Level Term (LLT), unless the reported CTCAE term is ‘Other – specify.’
- If the reported CTCAE term is ‘Other – specify,’ the MedDRA LLT, PT, and SOC centrally mapped from the verbatim AE term will be used.
- All listings and summaries will use the PT resulting from this process.

Preexisting conditions are defined as adverse events that begin prior to the first dose of study drug.

A treatment-emergent adverse event (TEAE) is defined as an event that first occurred or worsened in severity after baseline. Comparisons of preexisting conditions to on-treatment events at the LLT level will be used in the treatment-emergent computation.

The following summaries will be produced by PT within SOC: preexisting conditions, SAEs, TEAEs, drug-related TEAEs, and procedure-related TEAEs.

The following summaries will be produced by PT within SOC and maximum CTCAE grade: laboratory-based TEAEs, nonlaboratory-based TEAEs, drug-related laboratory-based TEAEs, and drug-related nonlaboratory-based TEAEs.

Reasons for death will be summarized separately for on-therapy and within 30 days of treatment discontinuation.

Hospitalizations and transfusions during the study treatment period or during the 30-day short-term follow-up period will be summarized by treatment group.

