Diarrhea Sections 9.4.1.1.4.1 and 9.6.5	Grade 3 or 4	Dose MUST be suspended until toxicity resolves to at least Grade 1.	Dose MUST be reduced by 1 dose level.
ALT/AST Increased Sections 9.4.1.1.4.2 and 10.3.3.1	Persistent or recurrent ^a Grade 2 (>3.0-5.0×ULN), or Grade 3 (>5.0-20.0×ULN) ^c	Dose MUST be suspended until toxicity resolves to baseline or Grade 1.	Dose MUST be reduced by 1 dose level.
ALT/AST Increased Sections 9.4.1.1.4.2 and 10.3.3.1	Grade 4 (>20.0×ULN)	Blinded study drug MUST be discontinued.	Blinded study drug MUST be discontinued.
ALT/AST Increased with increased total bilirubin, in the absence of cholestasis Section 9.4.1.1.4.2	≥Grade 2 increased ALT/AST (>3.0×ULN) with total bilirubin >2×ULN	Blinded study drug MUST be discontinued	Blinded study drug MUST be discontinued
ILD/Pneumonitis Sections 9.4.1.1.4.3 and 10.3.3.4	Grade 2 that persists or recurs despite maximal supportive measures and does not return to baseline or Grade 1 within 7 days	Dose MUST be suspended until toxicity resolves to baseline or Grade ≤1.	Dose MUST be reduced by 1 dose level.
ILD/Pneumonitis Sections 9.4.1.1.4.3 and 10.3.3.4	Grade 3 or 4	Blinded study drug MUST be discontinued.	Blinded study drug MUST be discontinued.
VTEs Sections 9.4.1.1.4.4 and 10.3.3.3	Grade 3 or 4	Suspend dose and treat as clinically indicated. May resume blinded study drug when participant is clinically stable.	Suspend dose and treat as clinically indicated. May resume blinded study drug when participant is clinically stable.

Abbreviations: ALT = alanine aminotransferase; ASCO = American Society of Clinical Oncology; AST = aspartate aminotransferase; ILD = interstitial lung disease; VTE = venous thromboembolic event.

Note: MUST = mandatory.

^a Determination of persistent events will be at the discretion of the investigator. Recurrent toxicity refers to the same event occurring within the next 8 weeks (as measured from the stop date of the preceding event). As a general guidance, based on the risk/benefit balance assessment per the investigator, for a patient who experiences a new episode of Grade 3 hematological toxicity after more than 8 weeks following the last episode of same Grade 3 hematological toxicity, the investigator may consider resuming the patient on the same drug dose should the patient satisfy the following conditions:

- shows stable hematological counts (Grade ≤2) during that timeframe
- has absence of any signs or risk of infection
- is benefiting from study treatment

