10.3.1. Adverse Events

Lilly has standards for reporting AEs that are to be followed regardless of applicable regulatory requirements that may be less stringent. A clinical study AE is any untoward medical event associated with the use of a drug or drug delivery system in humans, whether or not it is considered related to that drug or drug delivery system.

Lack of drug effect is not an AE in clinical trials, because the purpose of the clinical trial is to establish drug effect.

Any clinically significant findings from electrocardiograms (ECGs), labs, vital sign measurements, and other procedures that result in a diagnosis should be reported to Lilly or its designee.

Cases of pregnancy that occur during maternal exposures to study drug should be reported. Data on fetal outcome and breast-feeding are collected for regulatory reporting and drug safety evaluation.

Study site personnel will record the occurrence and nature of each patient's preexisting conditions, including clinically significant signs and symptoms of the disease under treatment in the study.

After the ICF is signed, site personnel will record the occurrence and nature of any AEs and any change in the preexisting condition(s). All AEs related to protocol procedures are reported to Lilly or its designee.

Investigators will be instructed to report to Lilly or its designee their assessment of the potential relatedness of each AE to protocol procedure and study drugs via eCRF.

The investigator will decide whether he or she interprets the observed AEs as related to disease, to the study medication, study procedure, or other concomitant treatment or pathologies. To assess the relationship of the AE to the study drug or procedure, the following terminologies are defined:

- **Probably related:** a direct cause and effect relationship between the study treatment and the AE is likely
- **Possibly related:** a cause and effect relationship between the study treatment and the AE has not been demonstrated at this time and is not probable, but is also not impossible
- **Does not know:** the investigator cannot determine
- **Not related:** without question, the AE is definitely not associated with the study treatment

The investigator should classify all "probably related," "possibly related," or "does not know" AEs and SAEs as related to study drug/study procedure.

Patients will be evaluated for AEs at each visit and will be instructed to call their physician to report any AEs between visits.

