Additional safety data should be collected via the case report form (CRF) if 1 or more of the following conditions occur:

In participants enrolled with baseline ALT or AST $1.5\times$ ULN

- Elevation of serum ALT or AST to $\geq 5\times$ ULN on 2 or more consecutive blood tests
- The combination of elevated ALT or AST $\geq 3\times$ ULN and elevated TBL $\geq 2\times$ ULN

In participants enrolled with baseline ALT or AST $\geq 1.5\times$ ULN

- Elevated ALT or AST $\geq 3\times$ baseline on 2 or more consecutive tests
- The combination of elevated ALT or AST $\geq 2\times$ baseline and elevated TBL $\geq 2\times$ ULN

In all study participants

- Discontinuation from study treatment due to a hepatic event or abnormality of liver tests
- Occurrence of a hepatic event considered to be an SAE

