10.4.1. Samples for Study Qualification and Health Monitoring

Blood samples will be collected to determine whether patients meet inclusion/exclusion criteria and to monitor patient health. Central hematology and chemistry labs may be drawn up to 3 days prior to Day 1 of each cycle. Enrollment and treatment decisions may be based upon results of tests performed locally. If local laboratory tests are used for this purpose, then a duplicate specimen must be submitted to the central laboratory. Discrepancies between local and central

laboratory that may have an impact on eligibility or treatment decisions will not be considered protocol deviations.

Investigators must document their review of each laboratory safety report.

Samples collected for specified laboratory tests will be destroyed within 60 days of receipt of confirmed test results. Tests are run and confirmed promptly whenever scientifically appropriate. When scientific circumstances warrant, however, it is acceptable to retain samples to batch the tests run, or to retain the samples until the end of the study to confirm that the results are valid. Certain samples may be retained for a longer period, if necessary, to comply with applicable laws, regulations, or laboratory certification standards.

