Attachment 6. Protocol JPBL Sampling Summary

This table summarizes the purpose for sampling, sample types, maximum volume per sample, maximum number of samples, and maximum total volume during the study. The summary below provides estimates. More samples could be required in the case of retests, additional health monitoring (if needed), or for patients continuing treatment beyond the protocol-specified number of cycles in the study. Fewer samples may actually be taken (for example, patients who discontinue from the study).

Protocol I3Y-MC-JPBL Sampling Summary^a

Purpose	Sample Type	Maximum Amount per Sample	Maximum Number Samples	Maximum Total Amount
Screening/Study qualification (Hematology and Clinical Chemistry)	Blood	7 mL	1	7 mL
Safety/Health monitoring (Hematology and Clinical Chemistry)	Blood	7 mL	11	77 mL
Pharmacokinetic sample	Blood	4 mL	6	24 mL
Pharmacogenetic blood sample	Blood	10 mL	1	10 mL
Biomarker plasma sample	Blood	10 mL	1	10 mL
Total blood volume	Blood			128 mL
Hepatic monitoring ^b	Blood	3 - 30 mL	-	-

^a Covers Cycles 1 through 9.

^b Based on laboratory safety values, unscheduled hepatic monitoring testing may be performed as part of patient follow-up, in consultation with the designated medical monitor.

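### Section 12.2.13 plans laboratory safety only as investigator-reported adverse-event tables; the documents supplied prespecify no by-arm summary of central values or of combined ALT/AST and bilirubin elevation

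*Protocol*

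**What the plan says.** **Analysis.** Section 12.2.13 starts from site reports: "The CTCAE v4 term reported by the investigator will be mapped to the MedDRA Preferred Term (PT) and System Organ Class (SOC"). Where the site picks the residual category, the term is coded centrally from the investigator's own words. The section adds: "All listings and summaries will use the PT resulting from this process". For laboratory findings it then lists one type of output, "The following summaries will be produced by PT within SOC and maximum CTCAE grade: laboratory-based TEAEs", and the same table restricted to events judged drug-related. The synopsis names adverse events as the only safety criterion.

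**Collection.** Section 10.4.1 states: "Central hematology and chemistry labs may be drawn up to 3 days prior to Day 1 of each cycle". The central panel in Attachment 2 includes blood counts, ALT, AST, and total and direct bilirubin. Attachment 6 gives a maximum of 1 screening and 11 safety samples over Cycles 1 to 9.

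**Site reporting.** Section 10.3.1 says: "Any clinically significant findings from electrocardiograms (ECGs), labs, vital sign measurements, and other procedures that result in a diagnosis should be reported". The definition of an adverse event in section 4 counts an abnormal laboratory result as a possible adverse event and does not require a diagnosis.

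**Liver.** Section 10.3.3.1 triggers extra case report form collection on several conditions. One, for patients with lower baseline transaminases, is: "The combination of elevated ALT or AST $\geq 3\times$ ULN and elevated TBL $\geq 2\times$ ULN". A second version, in multiples of baseline, covers patients who start at or above 1.5×ULN. Table JPBL.9.2 has a row for "≥Grade 2 increased ALT/AST (>3.0×ULN) with total bilirubin >2×ULN" where there is no cholestasis, and requires blinded study drug to be discontinued.

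**The concern.** The trial pays for regular, centrally measured laboratory data, but its stated safety analysis does not use them. It counts what investigators chose to report as adverse events.

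Two things follow. First, the protocol singles out a combined liver abnormality for retesting, extra data collection and a dosing rule, yet the stated analysis gives no count of it by arm. Second, the reported rate of any laboratory abnormality depends on when a site regards an abnormal value as reportable, and the protocol can be read two ways on that.

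At stake is the completeness of the randomized safety comparison. The primary PFS and the OS inference are not touched.

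**Working it through.** **1. Are central values really collected every cycle?** Attachment 6 states 11 safety samples through Cycle 9. Counting visits in Attachment 1: Cycle 1 Day 1 (1) + Cycle 1 Day 15 (1) + Day 1 of Cycles 2 to 9 (8) + short-term follow-up (1) = 11, an exact match. The schedule table is broken in the extracted text. Leaving out either Day 15 or follow-up gives 10. The blood volumes also add up: 7 + 77 + 24 + 10 + 10 = 128 mL, as stated. The every-cycle premise holds.

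**2. How much data is involved?** Screening plus safety samples: 1 + 11 = 12 per patient. Over 630 patients: 12 × 630 = 7,560. This is a ceiling. Attachment 6 gives maxima and says fewer samples may be taken, and 630 of the total are screening samples. The planning median PFS on control is 6.5 months, and 6.5 × 30.4 / 28 ≈ 7 cycles, so many patients would stop before Cycle 9.

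**3. Could the laboratory-based tables already be built from central values?** The text points the other way. The mapping from the investigator's term governs every listing and summary. The drug-related version needs a causality judgement, which section 10.3.1 assigns to the investigator for each event. No step in 12.2.13 grades a central value, and no shift or change-from-baseline table is named.

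**4. Can a table by term and maximum grade show the liver combination?** No. Suppose an arm of n patients has *a* patients with a transaminase term and *b* with a bilirubin term. The number with both lies anywhere from max(0, a + b − n) to min(a, b), and even that number says nothing about timing. Take the smallest case, a = b = 1:

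| What happened | Transaminase row | Bilirubin row | Patients with concurrent elevation |
|---|---|---|---|
| One patient, both raised at the same visit | 1 | 1 | 1 |
| One patient, raised in different cycles | 1 | 1 | 0 |
| Two different patients | 1 | 1 | 0 |

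The planned table is identical in all three. This does not depend on how completely sites report.

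**5. The two liver rules side by side.**

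| | Transaminase | Total bilirubin | Other condition | Consequence |
|---|---|---|---|---|
| 10.3.3.1, lower baseline | ≥3×ULN | ≥2×ULN | none | retesting; extra data collection |
| 10.3.3.1, baseline ≥1.5×ULN | ≥2×baseline | ≥2×ULN | none | retesting; extra data collection |
| Table JPBL.9.2 | >3.0×ULN | >2×ULN | no cholestasis | blinded study drug discontinued |

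The rules are closely similar but not the same, so any table must say which criterion it counts. No section says how the extra liver data will be summarized by arm.

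**6. Is undercounting shown?** Section 10.3.1 speaks of laboratory findings that lead to a diagnosis; the section 4 definition is wider. A site working from the first could leave out values that the second would count. The documents give neither abnormality rates nor reporting fractions, so no size can be calculated.

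**The case against.** **The main SAP may contain these tables.** The supplied SAP is an addendum on overall survival that cites SAP version 4, which is not in the package. Section 12.2.2 lets the SAP clarify methods and allows further exploratory analyses. This objection stands against the inference a reader might draw that the liver combination will never be reported, or that none of the cases will appear; the documents cannot support that. It does not remove the gap. Section 12.2.13 states a method and does not defer to the SAP, whereas 12.2.7, 12.2.8.1, 12.2.9, 12.2.12 and 12.2.15.2 do.

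**Abnormal values are already adverse events.** Section 4 says they can be, Table JPBL.10.3 asks for all adverse events, and section 10.4.1 requires investigators to document review of every laboratory safety report. The diagnosis sentence in 10.3.1 does not expressly exclude other findings. This also stands: a reader might infer that rates are undercounted, but the text shows only a risk. The risk is mainly in lower grades. Hematologic toxicity of Grade 3 or 4, persistent or recurrent Grade 2 ALT/AST elevation, and Grade 3 or 4 ALT/AST elevation all force suspension or discontinuation under Table JPBL.9.2, which is likely to prompt a report.

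**The liver combination is captured and watched.** It triggers retesting and dedicated data collection, reasons for discontinuation and dose adjustment are summarized, the sponsor physician reviews laboratory analytes, and the DMC sees unblinded safety data. All true. But the sponsor's review of deaths and serious events is blinded, group-level unblinding is reserved to the DMC, and the content of DMC outputs is not specified. None of this is a prespecified by-arm count in the final report. The optional modelling of blood counts in 12.2.10 is not a safety table either.

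**The combination is not uniquely serious.** A reader might take it as the protocol's gravest liver signal. The text does not say so: Grade 4 ALT/AST elevation alone also requires discontinuation, and a term-by-grade table can show that.

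**Conclusion.** The point holds in a limited form. In the documents supplied, laboratory safety is prespecified only through investigator-reported terms. No by-arm summary of central values and no table of concurrent ALT/AST and bilirubin elevation is planned. The concurrency gap is a matter of logic and rests on no assumption about reporting. It matters because the protocol itself defines the combination and collects data on it.

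In size, up to 12 central samples per patient through Cycle 9, at most 7,560 in all, have no safety summary stated for them. That figure is not an expected count and does not measure lost safety information. Undercounting of laboratory abnormalities is a plausible risk from two passages that need reconciling, and no magnitude can be attached to it.

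The conclusion assumes that the laboratory-based tables are built as the mapping rule in 12.2.13 reads. It is limited by the absence of the main SAP: if that document has the tables, what remains is a missing cross-reference. This should be corrected, but it changes no efficacy inference.

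**What to change.** Add the following to section 12.2.13, or cross-refer to the main SAP if it already has them:

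1. The number and percentage of patients per arm meeting the combined ALT/AST and bilirubin criteria of section 10.3.3.1, including the version in multiples of baseline. State the criterion in the table title, since Table JPBL.9.2 uses slightly different limits and a cholestasis condition. This is an analysis change only and proposes nothing about dosing.
2. By-arm shift tables from baseline to worst post-baseline CTCAE grade, derived from central values, for the main hematology and liver analytes: neutrophils, leukocytes, lymphocytes, hemoglobin, platelets, ALT, AST and bilirubin. Keep the adverse-event tables for attribution.
3. Reconcile section 10.3.1 with the adverse-event definition in section 4, so that sites work from one rule on when an abnormal laboratory value is reportable.

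The cost is plan wording and standard programming on data already collected; no new sample or visit is needed. Stated rates of laboratory abnormality may rise, and the report should explain that the two sets of tables have different sources.

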8.1. Summary of Study Design

Study I3Y-MC-JPBL (JPBL) is a multicenter, randomized, double-blind, Phase 3 trial for women with HR+, HER2- locally advanced or metastatic breast cancer. [Figure JPBL.8.1](#) illustrates the study design.

Abbreviations: HR+ = hormone receptor positive; HER2- = human epidermal growth factor receptor 2 negative; N = number; PD = progressive disease.

Figure JPBL.8.1. Illustration of study design.

Approximately 630 EP patients will be randomized 2:1 between the 2 arms:

- Experimental Arm A: abemaciclib 150 mg orally Q12H on Days 1 to 28 of a 28-day cycle plus fulvestrant 500 mg intramuscularly on Days 1 and 15 of Cycle 1, then on Day 1 of Cycle 2 and beyond
- Control (Placebo) Arm B: Placebo orally Q12H on Days 1 to 28 of a 28-day cycle plus fulvestrant 500 mg intramuscularly on Days 1 and 15 of Cycle 1, then on Day 1 of Cycle 2 and beyond

Enrollment will close when approximately 450 EP patients have been randomized at a starting dose of 150 mg Q12H. Patients will be randomized using the following stratification factors: nature of disease (visceral metastases versus bone only metastases versus other) and sensitivity to endocrine therapy (primary resistance versus secondary resistance). The presence of visceral metastases refers to lung, liver, pleural, or peritoneal involvement at the time of randomization. Primary clinical resistance to endocrine therapy is defined as follows: 1) for endocrine therapy in the adjuvant setting, recurrence within the first 2 years of adjuvant endocrine therapy while on endocrine therapy or 2) for endocrine therapy in the locally advanced or metastatic setting, progression within first 6 months of initiating first-line endocrine therapy while on endocrine therapy. Patients receiving prior endocrine therapy who do not meet the definition of primary clinical resistance will be considered to have secondary clinical resistance.

Data base lock for the interim analysis for efficacy will occur when approximately 265 investigator-assessed PFS events have been observed. Database lock for the final analysis of the PFS endpoint will occur when approximately 378 investigator-assessed PFS events have been observed. All patients will be followed for progression and survival information until death or study completion, whichever occurs first.

Details on sample size and analysis in Sections 12.1 and 12.2.

Terms used to describe the periods during the study are defined below:

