12.1. Determination of Sample Size

The primary objective of this study is to compare abemaciclib plus fulvestrant versus placebo plus fulvestrant in terms of PFS for women with HR+, HER2- locally advanced or metastatic breast cancer.

This study will enroll 2 strata of patients according to prior endocrine therapy: endocrine therapy pretreated (EP) patients and endocrine therapy naïve (EN) patients.

The primary statistical analyses will be performed on patients in the EP stratum.

The initial study protocol specified an enrollment of 450 EP patients. Amendment (a) changed the starting dose of blinded study drug from 200 mg Q12H to 150 mg Q12H. In addition to describing the safety profile in the full EP safety population, safety analyses will be conducted in the subgroup of patients enrolled under Amendment (a) with a starting dose of 150 mg Q12H. In order to do this robustly, enrollment to the study will continue until 450 EP patients are enrolled at a starting dose of 150 mg Q12H. As of the implementation of Amendment (a), approximately 180 EP patients had been enrolled at a starting dose of 200 mg Q12H. Including these 180 patients, the final size of the EP stratum will be approximately $450 + 180 = 630$ patients.

Patients will be randomized in a 2:1 ratio using the following stratification factors: nature of disease (visceral metastases versus bone only metastases versus other) and sensitivity to endocrine therapy (primary resistance versus secondary resistance).

A 2-look group-sequential design of the primary endpoint will be used to accommodate an event-driven plan for the interim and final PFS analyses (see Section 12.2.7 for details). The final PFS analysis will be performed after 378 PFS events have occurred in the EP stratum (that is, a 40% censoring rate). Assuming a hazard ratio (HR) of 0.703, this sample size yields approximately 90% statistical power to detect superiority of the abemaciclib plus fulvestrant arm over the placebo plus fulvestrant arm with the use of a 1-sided log-rank test and a type I error of 0.025. If the true median PFS for the placebo plus fulvestrant arm is 6.5 months, then the HR of 0.703 amounts to an approximately 2.75-month (42%) improvement in median PFS for the abemaciclib plus fulvestrant arm under an additional assumption of exponential survival distribution.

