12.2.12.4. Utilization

Utilization data will be summarized descriptively by category across arms (for example, analgesic use, bisphosphonate use, transfusions, radiation, surgery, and hospitalization days), including a frequency table with tabular statistics. For categorical variables, frequency and the corresponding percentage will be derived and measures of central tendency and variability will be calculated for continuous variables by arm. Tests for differences in proportion between treatment groups and between response groups will be performed.

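### By-arm summaries and tests of proportions for hospitalizations and transfusions ignore longer treatment on abemaciclib, so equal event rates would appear as a modest excess; exposure-adjusted rates and a time-to-first-event analysis should be added

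*Protocol*

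**What the plan says.** Protocol Section 12.2.13 lists SAE and TEAE summaries by Preferred Term within System Organ Class. It also has "Hospitalizations and transfusions during the study treatment period", or in the 30-day follow-up, summarized by treatment group. Exposure and the number of patients completing each cycle are separate descriptive summaries. No exposure-adjusted rate, fixed window or time-to-event analysis is named for these outcomes.

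Section 12.2.12.4 covers analgesic and bisphosphonate use, transfusions, radiation, surgery and hospitalization days, and adds: "Tests for differences in proportion between treatment groups and between response groups will be performed". Section 12.2.2 sets the default at 2-sided 0.05. Section 10.2.2 has these data collected during the study and at the 30-day visit.

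Treatment continues until progression or another discontinuation criterion (Synopsis; Section 7.3.1). Section 12.1 takes a control median PFS of 6.5 months and expects an "approximately 2.75-month (42%) improvement in median PFS" on abemaciclib, under exponential survival.

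**The concern.** The period in which a hospitalization or transfusion can be counted ends 30 days after treatment stops, and treatment is expected to last longer on abemaciclib. A patient observed longer has more opportunity for a first event. If the event rate per month were identical in the two arms, the proportion with at least one event would still be higher on abemaciclib. The separate exposure table lets a reader see the imbalance but corrects neither the percentages nor the test.

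At stake is how the safety and utilization tables are read. An excess of hospitalization or transfusion that comes only from longer disease control could be taken as toxicity, and the planned test could support that reading at more than its nominal error rate. The primary PFS result is not affected.

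**Working it through.** **1. Design figures (Section 12.1).** The plan states: "Assuming a hazard ratio (HR) of 0.703, this sample size yields approximately 90% statistical power". The other inputs are 378 events, 2:1 allocation and 1-sided alpha 0.025.

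- Power = Φ(√(378 × 2/3 × 1/3) × |ln 0.703| − 1.960) = Φ(3.230 − 1.960) = 89.8%. This agrees with the plan.
- Median on abemaciclib = 6.5/0.703 = 9.25 months, a gain of 2.75 months; 1/0.703 − 1 = 42%. This also agrees.
- Monthly progression hazards: placebo μ = ln 2/6.5 = 0.1066; abemaciclib 0.703 × 0.1066 = 0.0750.

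**2. Follow-up at the planned final PFS analysis.** 378 events in 630 patients leaves 1 − 378/630 = 40% censored. With common follow-up C, solve (2/3)(1 − e^(−0.0750C)) + (1/3)(1 − e^(−0.1066C)) = 0.60. This gives C ≈ 10.9 months. Mean treatment time is (1 − e^(−μC))/μ: 6.43 months on placebo and 7.43 on abemaciclib, a ratio of 1.16. Only if everyone is followed to progression are the means 9.38 and 13.34 months, a ratio of 1.42.

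**3. Crude proportions when the rates are equal.** Assumptions: treatment time equals PFS; constant event rate L, the same in both arms; L = 0.02 and 0.03 per month (assumed, since the documents give none). With w = 30 days = 0.986 months, time at risk is treatment time plus w, cut at C:

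P = 1 − [e^(−Lw) × μ/(L+μ) × (1 − e^(−(L+μ)(C−w))) + e^(−μ(C−w)) × e^(−LC)]

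Example for L = 0.02, C = 10.86:
- Placebo: 1 − [0.980 × 0.842 × 0.714 + 0.349 × 0.805] = 13.0%.
- Abemaciclib: 1 − [0.980 × 0.789 × 0.609 + 0.477 × 0.805] = 14.5%.

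**4. Rejection probability.** Two-sided 0.05 pooled two-proportion test, 420 versus 210 patients, normal approximation. In the example, the difference is 0.015, the standard error is 0.0293 under the null and 0.0289 otherwise, and the test rejects 8% of the time.

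| Follow-up | L per month | Abemaciclib | Placebo | Ratio | Rejects |
|---|---|---|---|---|---|
| 10.9 months (40% censored) | 0.02 | 14.5% | 13.0% | 1.12 | 8% |
| | 0.03 | 20.8% | 18.7% | 1.11 | 9% |
| 24 months | 0.02 | 20.3% | 16.6% | 1.22 | 19% |
| | 0.03 | 28.2% | 23.3% | 1.21 | 25% |
| All to progression | 0.02 | 22.6% | 17.4% | 1.30 | 32% |
| | 0.03 | 30.7% | 24.2% | 1.27 | 39% |

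Replacing common follow-up by uniform accrual over 16 to 20 months (assumed), with the cut still at 40% censoring, gives 8% to 11%.

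**5. Sensitivity.**
- *Smaller treatment-time gap.* With L = 0.03 and full follow-up, rejection against abemaciclib falls from 39% at a mean-treatment-time ratio of 1.42 to 13% at 1.2 and 6% at 1.1.
- *Early events.* If events occur only in the first 56 days at 0.10 per month, the proportions are 16.6% and 16.5% and the test keeps its 5%.

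**6. Check on a constant-rate model.** Suppose identical events confined to the first month. Counts per patient are then equal, so the rate ratio per treatment month is the inverse of the treatment-time ratio: 6.43/7.43 = 0.87 at the planned censoring and 9.38/13.34 = 0.70 with full follow-up. The longer-treated arm would look safer than it is.

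**The case against.** Four points on the other side carry weight.

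- *Size.* A reader might infer from the 42% gain in median PFS that abemaciclib patients are observed 42% longer, and that harm is overstated in the same proportion. The documents do not support this. The final PFS analysis is planned at 40% censoring, where mean treatment time differs by about 16% and the risk ratio is 1.11 to 1.12. Even with full follow-up the ratio is 1.27 to 1.30. PFS is also not treatment time: Sections 7.3.1 and 9.4.1.1 let or require patients to stop for other reasons, including toxicity.
- *Validity of the test.* A reader might infer that the test of proportions has no valid error rate. It is valid for its own null, equal cumulative proportions, and total burden per patient is a legitimate question for resource use. It is miscalibrated only when read as a test of equal event rates.
- *Silence.* Section 12.2.12 refers further detail to the SAP. The supplied SAP text is an overall-survival addendum that points to SAP v4. An adjusted analysis there cannot be excluded. Section 12.2.13 also gives no metric for its hospitalization summary, and Section 12.2.12.4 lists hospitalization days without saying which proportion is tested.
- *The obvious remedy.* Replacing the test with a Poisson or negative-binomial model with a log-exposure offset assumes a constant rate. Section 5.1.1 reports that dose alterations came mainly from first-cycle diarrhea, and such events would be biased toward abemaciclib (step 6).

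All four limit the point. None removes it: the protocol itself commits to the tests of proportions, and for events that accrue over treatment the direction of the bias is clear.

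**Conclusion.** The point holds as a low-cost improvement. For events that accrue over treatment, the named summaries and tests would show a modest excess on abemaciclib when the true rates are equal. The nominal 5% test rejects about 8% to 9% of the time at the planned 40% censoring and 19% to 25% at 24 months. The 32% to 39% obtained with every patient followed to progression is a ceiling.

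These figures rest on the design's hazard ratio and control median, exponential PFS, treatment time equal to PFS, and assumed rates of 0.02 to 0.03 per month. Toxicity discontinuation on abemaciclib would lower them. Early-onset events are barely affected. For TEAEs and SAEs the issue is interpretation only, because no test of them is planned.

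**What to change.** First check whether SAP v4 already provides this. If it does not:

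- In Section 12.2.13, keep the crude percentages and add exposure-adjusted incidence rates per 100 patient-years for hospitalizations, transfusions, SAEs and TEAEs of Grade 3 or higher.
- In Section 12.2.12.4, keep the test of proportions and add beside it a time-to-first-event comparison for hospitalization and for transfusion: cumulative incidence curves with a log-rank test or Cox model. Section 12.2.12.6 already plans a log-rank comparison for skeletal-related events. Do not substitute a constant-rate Poisson offset model.

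The cost is a few tables and curves from data already collected. There is a second set of figures to explain. Rates per patient-year understate front-loaded toxicity in the longer-treated arm, so they must be read beside the crude percentages. Section 12.2.2 allows minor method changes in the SAP before the aggregate database is unblinded, and provides for other changes to be described and justified in the clinical study report.
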